9.5.2 Secondary Outcomes

The **secondary outcomes** of interest are pain level, pain-related functioning, and frequency of substance use. We hypothesize that participants receiving the PPMI condition (intervention condition) will report less pain, an increase in pain-related functioning, and lower frequency of substance use over the 3-month (Secondary Aim 2) and 12-month (Secondary Aim 3) follow-up period when compared to the EUC condition (control condition).

These outcomes for both **Secondary Aims 2 and 3** will be measured in the following ways:

- **Pain level** will be measured using the Numerical Rating Scale for Pain Intensity (NRS-I), which will be collected at all time-points. For each follow-up time point, we will subtract the baseline value to obtain a change score. For this study, a clinically significant change in pain level will be operationalized as a 30% reduction of pain, which would equate to change of 2 points on a 0 to 11 pain intensity numerical scale such as the NRS-I.
- **Pain-related functioning** will be measured using the pain interference subscale of the Brief Pain Inventory – Short Form (BPI). The BPI Short Form is a widely used, validated measure that assesses both pain level and the impact pain has on functioning over the past 24 hours. For each follow-up time point, we will subtract the baseline value to

obtain a change score. For this study, an increase in pain-related functioning will be operationalized as a reduction in the pain interference scale scores over time.

- **Frequency of substance use** will be measured using the TLFB, which will be collected at all follow-up time-points. During this administration, the participant will be asked to recall their alcohol and drug use since the previous follow-up time point. Percent days abstinent from alcohol and drugs will be used as the primary measure of substance use at each assessment time point (baseline, 1-, 3-, 6-, 9-, and 12-month follow-up assessment).

To accomplish **Secondary Aim 4** (qualitative interviews for rapid implementation), a random sample (n=20) of participants who completed the PPMI condition will be interviewed in addition to a sample (n=15) of buprenorphine providers/clinic staff.

9.6 Data Analyses

This study will utilize an intent-to-treat approach where the primary analyses will examine the association between randomization to condition and the treatment outcomes, irrespective of how much of the intervention or control conditions the participants attended. However, in exploratory analyses, the study will explore how controlling for session attendance influences the primary results and whether session attendance mediates the potential effects of assignment to treatment condition on the subsequent outcomes. The PI, data manager, and project biostatisticians and/or data analysts will analyze the data using SAS software. The primary specific aims will focus on pain (level, tolerance and pain-related disability) and substance use (frequency of drug, alcohol and opioid use) outcomes. Outcome data will be analyzed using mixed model regression analyses. The alpha level will be set at 5%.

As stated previously, the primary aims are:

Primary Aim 1: Conduct a randomized controlled trial (RCT) comparing a remotely delivered PPMI (n=100) to EUC (n=100) to assess the impact of randomization to PPMI on retention on buprenorphine treatment over 3-months.

Research Hypotheses for Primary Aim 1: Participants in the PPMI condition will have greater retention on buprenorphine treatment (i.e., lower treatment dropout): up to 3-months. The primary goals for the project are to test the preliminary efficacy of an 8-session Psychosocial Pain Management Intervention (PPMI), as compared to an EUC control condition, on retention on buprenorphine treatment. We will evaluate measures of self-reported information gained from the TLFB on buprenorphine treatment use on a daily basis and data collected from weekly surveys completed by the participant. For those with multiple sources of information available (TLFB and self-report survey), we will use the comparison between sources of data to develop reasonable assumptions about actual consumption. It is anticipated that individuals will occasionally miss a day of buprenorphine treatment without having dropped out of treatment. Discontinuation of treatment will be operationalized as 7 days in a row without taking buprenorphine. Analysis will follow a time-to-event (survival analysis) framework where the outcome is time until discontinuing buprenorphine treatment.

We will first descriptively calculate the percent still receiving buprenorphine at the 1- and 3-month follow-ups. The independent variable of interest is an indicator of group (PPMI vs.

EUC). Analysis will use an intent-to-treat framework, where participants are classified by the condition they were randomized to, regardless of what they received. Cox Proportional Hazards regression models will be used to test the association between group assignment and time to dropping out of buprenorphine treatment at 3-months. We will test if assumptions for this modeling technique are met, and if they are not, consider including a covariate*time interaction or stratification in Cox modeling, or variable transformations or alternative modeling strategies, if necessary.

The secondary aims are:

Secondary Aim 1: Conduct a randomized controlled trial (RCT) comparing remotely delivered PPMI (n=100) to EUC (n=100) to assess the impact of randomization to PPMI on retention on buprenorphine treatment over 12-months.

Secondary Aim 2: Determine the impact of remotely delivered PPMI on pain level, pain-related functioning, and frequency of substance use over 3-months.

Secondary Aim 3: Determine the impact of remotely delivered PPMI on pain level, pain-related functioning, and frequency of substance use over 12-months.

Research Hypotheses for Secondary Aim 1: Participants in the PPMI condition will have greater retention on buprenorphine treatment (i.e., lower treatment dropout) over the entire 12-months of follow-up. The primary goals for the project are to test the preliminary efficacy of an 8-session Psychosocial Pain Management Intervention (PPMI), as compared to an EUC control condition, on retention on buprenorphine treatment. We will evaluate measures of self-reported information gained from the TLFB on buprenorphine treatment use on a daily basis and data collected from weekly surveys completed by the participant. For those with multiple sources of information available (TLFB and self-report survey), we will use the comparison between sources of data to develop reasonable assumptions about actual consumption. It is anticipated that individuals will occasionally miss a day of buprenorphine treatment without having dropped out of treatment. Discontinuation of treatment will be operationalized as 7 days in a row without taking buprenorphine. Analysis will follow a time-to-event (survival analysis) framework where the outcome is time until discontinuing buprenorphine treatment.

We will first descriptively calculate the percent still receiving buprenorphine at the 6-, 9-, and 12-month follow-ups. The independent variable of interest is an indicator of group (PPMI vs. EUC). Analysis will use an intent-to-treat framework, where participants are classified by the condition they were randomized to, regardless of what they received. Cox Proportional Hazards regression models will be used to test the association between group assignment and time to dropping out of buprenorphine treatment at 12-months. We will test if assumptions for this modeling technique are met, and if they are not, consider including a covariate*time interaction or stratification in Cox modeling, or variable transformations or alternative modeling strategies, if necessary.

Research Hypotheses for Secondary Aims 2 and 3: Compared with participants randomized to the EUC (control) condition, participants randomized to the PPMI condition will report a greater reduction in pain level, an increase in pain-related functioning, and a decrease in frequency of substance use at: (1) 3-months; and (2) 12-months post-intervention. We will calculate the

means and standard deviations for these outcomes at baseline, 1-, 3-, 6-, 9-, and 12-months, as well as change scores from baseline for the two groups. We hypothesize that participants randomized to the PPMI will have less pain, better functioning, and lower frequency of opioid use at follow-ups compared to EUC. These secondary outcomes are hypothesized to meet the assumptions of continuous variables, and we will consequently use t-tests to make comparisons. If, however, the distribution of a given outcome measure is skewed, alternative modeling strategies will be used. We will use a linear mixed-effects model and estimate the treatment effect as the difference in the time-averaged changes from baseline in pain levels (using the NRS-I) and in pain-related functioning (using the BPI) over the course of follow-up (namely, at 3-months for secondary aim 2 and at 12-months for secondary aim 3). Because reduction in pain is of key interest, the analysis will model change-scores from baseline in the response variable as the dependent variable, and the independent variables will include the baseline values of the response variable, time in months since randomization and the treatment group indicator. The parameter estimate of the treatment group indicator will estimate the time-averaged treatment effect. If the graphical exploration (described above) shows potentially differential linear decrease in pain over time, we will include an interaction of time by treatment group indicator to model and test for this. For frequency of substance use, we will first assess the distribution of measures collected to assess alcohol use, illicit drug use and prescription opioid medication use to determine whether a summary or composite measure of each of these may represent the use or misuse more appropriately. For example, illicit drug use will be obtained as the number of days the participant used each of multiple drugs, and thus we may consider combining the days of any of the illicit drug use. We will also combine the alcohol and drug use data obtained using TLFB interviews as the percent days abstinent from alcohol and drugs during the past 30 days at each assessment time. We will then check the distribution of the substance use and prescription medication misuse (measured using the TLFB), and unless the data are highly skewed, we will use a linear mixed-effect model to test the hypothesis and to estimate the treatment effect as the difference in the time-averaged changes from baseline in these outcome measures over the course of the 12-month follow-up period.

Secondary Aim 4: Facilitate the rapid implementation of results by gathering qualitative data from key stakeholders including MAT treatment providers (n=15) and patients who received the telehealth PPMI condition (n=20).

Research Hypothesis for Secondary Aim 4: We will follow a comprehensive plan to integrate quantitative and qualitative data to more rapidly enable future implementation of the intervention in patients receiving buprenorphine for OUD. First, this study is a mixed-methods hybrid type I study specifically guided by the widely-used RE-AIM framework, which provides essential elements to consider to understand barriers and facilitators to future implementation. We will address key specific questions that we will be able to answer through our qualitative and quantitative data and how they will inform our understanding of future implementation as guided by the specific elements of RE-AIM. Second, we are using a rapid analysis approach in our qualitative interviews, a specific deductive approach using semi-structured interviews to produce actionable information from qualitative data in a timely manner. We will organize the summarized qualitative data using matrices, which will increase efficiency of analyzing the data and synthesizing overall findings. Finally, our team has extensive methodological expertise in conducting mixed-methods substance use disorder intervention studies to enhance future implementation.

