4.1 Inclusion Criteria

Participant responses to study measures will be evaluated by research staff to ensure all eligibility criteria are met before participants are enrolled into the full RCT. Participants will complete a brief eligibility screening survey to ascertain appropriateness for the study. Any questions pertaining to participant responses will be clarified with the participant prior to the determination of eligibility status. The ability to understand study procedures and to comply with them for the entire length of the study will be assessed prior to enrollment in the trial.

Inclusion criteria for the main RCT trial are:

- (a) at least legal adult age to consent without a guardian ((18 years of age or older in all states except Alabama (requires 19 years of age), Nebraska (requires 19 years of age), and Mississippi (requires 21 years of age))
- (b) having a diagnosis of an OUD within the past 12 months;
- (c) started buprenorphine (*the term we use to refer to all buprenorphine products including buprenorphine/naloxone*) treatment within the past 6 months
- (d) at least moderate or greater self-reported pain on average over the past 3 months;
- (e) regular and consistent access to a telephone and willingness to use the phone for study telephone sessions.

Participants in this study will be of legal adult age to consent without a guardian (18 years old or older in most states unless in Alabama (requires 19 years of age), Nebraska (requires 19 years of age) and Mississippi (requires 21 years of age) for several reasons. All participants will be patients prescribed buprenorphine for the treatment of an OUD who also experience pain. Due to the differences in pain management and intervention strategies for those 17 and younger relative to older individuals, a separate study would be required to appropriately examine opioid safety among children and adolescents age 17 and under with pain. Individuals age 18 to 20 will be included in the study because individuals in this age range receive medical care services related to OUD and pain in the same manner as those individuals age 21 and older.

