 - The Numeric Rating Scale of pain intensity (NRS-I) is an 11-point numeric rating scale (0 = no pain, 10 = worst pain imaginable) widely used in medical settings to assess global pain intensity.
- Current buprenorphine prescription (*multiple response options*)
- Route of administration for buprenorphine medication (*multiple response options*)
- Opioid use disorder diagnostic screen (*measured by the RODS*).
 - The Rapid Opioid Dependence Screen (RODS) is an 8-item measure designed to screen for opioid dependence.

Once the participant completes the eligibility survey, responses will be reviewed to assess for potential eligibility. For those participants who are ineligible, their participation in the study will be complete at this time. No identifiable information or contact information

will be collected from those participants who screen ineligible, or from those participants who screen eligible but report no interest in continuing on with the research study. All eligibility criteria will be confirmed, including most recent buprenorphine treatment episode start date and self-reported use of prescribed buprenorphine within 10 days of the enrollment interview, with the participant prior to the participant being enrolled in the study. Participants will have 60 days from the date the eligibility screening is completed to schedule and complete the baseline enrollment assessment. Eligible participants who do not complete enrollment within that time frame will be considered to have declined to participate in the full RCT.

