9.2 Sample Size and Randomization

Sample size estimates were guided by our prior work on psychosocial interventions for pain during addiction treatment and prior trials that used MAT retention as an outcome and calculated using Stata. In studies of buprenorphine programs, retention varies widely but generally is around 50% in studies with at least 3-months of follow-up and robust sampling.²⁶ For a time-to-event analysis we assumed an event rate of 50% in EUC, where the event is dropping out of treatment, and based calculations on a two-sided $\alpha=0.05$. A hazard ratio of 0.5 (i.e., PPMI less likely to drop out of treatment) would achieve >85% power with a sample size of 200, or 100 per group. Given that we will be able to infer treatment retention even for participants who drop out of the study, our primary outcome analysis was based around our complete sample size of 200.

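### Time already on buprenorphine at entry (0 to 6 months) is known for everyone but not named in either Cox model; pre-specifying it would cost nothing and protect power if it is strongly prognostic

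*Combined protocol and SAP*

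**What the plan says.** Section 4.1 admits people who started buprenorphine "treatment within the past 6 months", and a lapse of at least 30 days starts a new episode. Retention is then followed from enrolment for everyone, wherever they are in that episode.

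Section 6.2.1 has staff confirm all eligibility criteria before enrolment, "including most recent buprenorphine treatment episode start date". Section 6.2.2 repeats this check and also lists length of treatment among the baseline questionnaire topics. The variable is therefore a baseline measure and not only an eligibility item.

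For the 3-month and the 12-month Cox models, Section 9.6 states that "The independent variable of interest is an indicator of group" and lists no other term. Covariate-by-time terms or stratification appear only as remedies if model assumptions fail. Section 9.3 names no covariate either. Randomisation is stratified by sex, past-year heroin use and veteran status (Section 9.2.1).

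Section 5.1 (Treatment as Usual) says that treatment experiences are recorded so that confounding can be handled in analysis. It names no variable and no model.

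For power, Section 9.2 says "we assumed an event rate of 50% in EUC, where the event is dropping out of treatment", takes a hazard ratio of 0.5, and concludes that this "would achieve >85% power with a sample size of 200, or 100 per group".

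**The concern.** The trial pools people in their first days of treatment with people who have already stayed for months. If early drop-out is more frequent than later drop-out, time on treatment at entry predicts the event.

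Leaving a prognostic variable out of a Cox model does not invalidate the randomised comparison. It does move the group hazard ratio towards 1 relative to the hazard ratio at a fixed time on treatment, and it can cost power. It also leaves any chance difference between arms in time on treatment uncorrected, because the stratification does not balance that variable.

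There is a pre-specification side too. Section 9.1 promises that the main analyses are planned in advance, while the general remark in Section 5.1 leaves open which variables, if any, enter the primary model. For the mixed models of pain, by contrast, Section 9.6 does list the covariates.

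**Working it through.** **1. Reproduce the plan's figure.** Inputs from Section 9.2: 100 per arm, EUC event rate 50%, hazard ratio 0.5, two-sided alpha 0.05.

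- EUC events: 100 × 0.50 = 50.
- PPMI events: 100 × (1 − 0.5^0.5) = 29.3. Total 79.3.
- Schoenfeld: power = Φ(½ × √79.3 × |ln 0.5| − 1.96) = Φ(3.086 − 1.96) = 87.0%.
- Freedman: Φ(√79.3 × 0.5/1.5 − 1.96) = 84.3%.

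The stated figure is reproduced, with about 2 points to spare by Schoenfeld. Keeping the same formula and the EUC rate at 50%, a hazard ratio of 0.51 gives 85.3% and 0.52 gives 83.4%.

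**2. Is the variable plausibly prognostic?** Section 2.1 puts retention near 50% at 3 months, and Section 4 puts one-year drop-out at one VA site above 50%. A constant hazard with 50% lost at 3 months would imply 1 − 0.5^4 = 94% lost at one year, so any one-year figure between 50% and 94% fits a falling hazard. The populations differ and the one-year figure is only a lower bound. This supports plausibility and does not supply a gradient.

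**3. Simulate with an assumed gradient.** Assumptions, none of them from the documents: entry time x uniform over 0 to 6 months; EUC hazard λ × m^x, where m is the multiplier per month already on treatment; PPMI hazard half of that at every x (a conditional hazard ratio of 0.5); λ set so that EUC drop-out averages 50% at 3 months; censoring at 3 months. There were 10,000 trials per scenario with 100 per arm. Each was fitted with group alone and with group plus x. The large-sample hazard ratio comes from one simulated set of 400,000.

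| m per month | Fold change over 6 months (1/m^6) | EUC 3-month drop-out, entry at month 0 / month 6 | Large-sample unadjusted HR | Power, group only | Power, adjusted |
|---|---|---|---|---|---|
| 1.0 | 1.0 | 50% / 50% | 0.50 | 85.4% | 85.6% |
| 0.9 | 1.9 | 61.2% / 39.5% | 0.50 | 85.0% | 85.5% |
| 0.85 | 2.7 | 67.2% / 34.3% | 0.50 | 84.3% | 85.9% |
| 0.8 | 3.8 | 73.4% / 29.3% | 0.51 | 82.9% | 85.8% |
| 0.75 | 5.6 | 79.5% / 24.6% | 0.52 | 82.4% | 86.3% |
| 0.7 | 8.5 | 85.3% / 20.2% | 0.53 | 80.0% | 86.7% |

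The Monte Carlo standard error is about √(0.85 × 0.15 / 10,000) = 0.4 points. Two smaller simulations agree. One (2,500 trials) gave 85/85%, 84/86% and 81/87% at 2-, 4- and 8-fold. The other (3,000 trials) gave 86/86%, 86/86%, 84/86% and 80/86% at m = 1.0, 0.9, 0.8 and 0.7.

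**4. Chance imbalance.** With uniform entry, the SD of x is 6/√12 = 1.73 months, and the standard error of the between-arm difference in means is 1.73 × √(2/100) = 0.24 months. At m = 0.8, an imbalance of 1.96 standard errors (0.48 months) moves the hazard ratio by a factor of about exp(0.223 × 0.48) = 1.11. A true 0.50 could then appear as roughly 0.45 or 0.56.

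**5. If 0.5 is the marginal hazard ratio.** The group-only test then estimates exactly what was planned for. Its power is the 87.0% of step 1, and adjustment can only add to that.

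**The case against.** A reader might infer that the omission makes the stated power wrong, or that any realistic spread in time on treatment pulls it below 85%. The documents do not support this. They give no prognostic strength for the variable, and Section 9.2 does not say whether 0.5 is marginal or conditional. Up to about a 2-fold gradient the loss is at most 0.5 points, which is within simulation error. With no gradient at all, Freedman gives 84.3% and simulation 85.4%, so a small shortfall around 85% depends as much on the formula as on the model.

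A reader might also infer that the variable was deliberately excluded. The wording in Section 9.6 identifies the variable of interest and does not say it is the only term, and Section 5.1 signals some intention to adjust. The accurate criticism is that the covariate is unspecified.

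Three further objections have force. The protocol cites evidence of differing retention for sex and heroin use, and it stratifies on both; no such evidence is cited for time on treatment. The 30-day lapse rule mixes first-time starters with people resuming treatment, so a single linear term may recover less than the table shows. And the simulation holds EUC events at 50%. If people already months into treatment drop out less, that rate itself may be lower: at 45%, 40% or 30%, Schoenfeld power is 83.1%, 78.3% or 65.5%. That is a separate matter, which this covariate would not repair.

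What remains is that both models name no baseline covariate, the data are already collected, and adjustment cost no power in any scenario examined.

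**Conclusion.** The point holds as a recommended improvement and not as an error in the power calculation. The group-only test is valid. If 0.5 is conditional and EUC events are 50%, adjustment makes no material difference up to about a 2-fold gradient over 6 months. It is worth about 2 to 3 points at about 4-fold and about 6 to 7 points at about 8-fold. If 0.5 is marginal, the stated figure stands and adjustment is an extra gain. In either case it corrects for chance imbalance in a variable that the stratification does not control, and it settles in advance a choice now left open.

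These sizes rest on uniform entry times, a log-linear gradient and 3-month follow-up. No calculation was made for the 12-month model; the same reasoning applies there, but its size is unknown.

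**What to change.** In Section 9.6, add months since the start of the current buprenorphine episode (continuous, measured at baseline from the confirmed start date) as a pre-specified covariate in the 3-month and 12-month Cox models. Show its distribution by arm in the baseline table. State that the reported hazard ratio is conditional on that covariate, and say in Section 9.2 whether the planned 0.5 is meant as marginal or conditional.

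The cost is a line or two of text and one degree of freedom. No new data are needed, and the sample size does not change.
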